Convalescent Plasma in the Early Treatment of High Risk Patients with SARS-CoV-2 (COVID-19) Infection Protocol

NCT04513158

Amendment 1.0, Version 31 AUG 2020

Convalescent Plasma in the Early Treatment of High-Risk Patients with SARS-CoV-2 (COVID-19) Infection

PROTOCOL Amendment 1.0 (Version 31 AUG 2020)

Protocol Number 20-N0124**IND Number** 23679**Principal Investigator:** [name]
Norton Healthcare
[name]
[name]
[contact]
[contact]**Norton Co-Investigators:** [name]
[name]
[name]
[name] [name]**Nurse Coordinator** [name]**Therapy:** COVID-19 Convalescent Plasma Infusion

SCHEMA

Treatment Plan

High Risk Patient Selection

Must have the Following	1 unit (Approximately 200 mL) of Convalescent Plasma over 60 minutes

 • Diagnosis of SARS-CoV-2 infection via RT-PCR or FDA approved testing. 
Patients must also have the following indications for enrollment:
 
 • D-Dimer > 500 ng/ml FEU OR • IL-6 > 5 pg/mL 
With any of the following
 
 • Lymphocytes < 0.8 10^3/ul OR • LDH > 700 U/L OR • CK > 170 U/L OR • CRP > 1.0 mg/dl OR • Ferritin > 1000 ng/ml 
AND one of the following:
 
 Age over 60 years Underlying Active Malignancy Cardiovascular Disease Active Tobacco Use History of Pulmonary Volume Reduction Surgery Hypertension 	

Table of Contents

Contents

1.0	OBJECTIVES.....	5
2.0	BACKGROUND AND RATIONALE.....	5
3.0	RATIONALE FOR STUDY SCHEDULE.....	8
4.0	PATIENT SELECTION.....	8
5.0	DONOR INFORMATION	10
7.0	PROCEDURES FOR PATIENT ENTRY ON STUDY	11
8.0	DOSE MODIFICATION FOR OBESE PATIENTS.....	13
9.0	CRITERIA FOR RESPONSE ASSESSMENT	13
10.0	MONITORING OF PATIENTS.....	13
11.0	STATISTICAL CONSIDERATIONS.....	14
12.0	DATA REPORTING / REGULATORY REQUIREMENTS.....	15
13.0	ADVERSE EVENTS AND REPORTING REQUIREMENTS.....	15
14.0	REFERENCES	18
15.0	TABLE 1: DEFINING CHARACTERISTICS OF SEVERE COVID-19 DISEASE	21
16.0	APPENDICES.....	21

1.0 OBJECTIVES

1.1 Primary Objectives:

To determine the therapeutic efficacy (response rate) of convalescent plasma infusion in patients at high risk for mortality when infected by SARS-CoV-2 (COVID-19). The primary endpoint will be determined as prevention of progression to severe or life threatening COVID-19 during the current hospitalization. The primary endpoint will be assessed at discharge and by evaluating if the patient experienced the following data elements: respiratory rate >30/min, Blood oxygen saturation <93%, partial pressure of arterial oxygen to fraction of inspired oxygen ration <300, or received a medical diagnosis of respiratory failure, septic shock or multiple organ dysfunction/failure. This will be captured from the daily physical exam/clinical assessment done as part of routine care. See table 1.

1.2 Secondary Objectives

- 1.2.1 To determine the immunologic effects of convalescent plasma infusion as measured by serial SARS-CoV-2 Ag levels through RT-PCR. This will be measured by CoV PCR collected at enrollment, day 7 and discharge.
- 1.2.2 To measure normalization of laboratory parameters for risk as referenced in Appendix 2. Lab values outlined in appendix 2 will be documented every 3 days while the patient is hospitalized and we will evaluate labs from the time of convalescent plasma infusion to the time that lab value returns to within the institution's normal range.

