4.0 PATIENT SELECTION

4.1 Eligibility Criteria

4.1.1 Diagnosis of SARS-CoV-2 infection via RT-PCR or FDA approved testing.

4.1.2 Patients must also have the following indications for enrollment:

- i. D-Dimer > 500 ng/ml FEU **OR**
- ii. IL-6 > 5 pg/mL

With any of the following

- iii. Lymphocytes < 0.8 10^3 /ul **OR**
- iv. LDH > 700 U/L **OR**
- v. CK > 170 U/L **OR**
- vi. CRP > 1.0 mg/dl **OR**
- vii. Ferritin > 1000 ng/ml

AND one of the following:

- viii. Age over 60 years
- ix. Underlying Active Malignancy
- x. Cardiovascular Disease
- xi. Active Tobacco Use
- xii. History of Pulmonary Volume Reduction Surgery
- xiii. Hypertension

4.1.3 Prior Treatment: Patients are still eligible for this trial if active antimicrobial agents are in use. Patients are also eligible if they had been treated on COVID-19 clinical trial in the course of their disease.

4.1.4 Age \geq 18 years.

4.1.5 The effects of allogeneic plasma infusion on the developing fetus is unknown. For this reason women who are pregnant are not eligible to participate.

4.1.6 Agrees to required laboratory data collected which will include the baseline organ function and regular ongoing assessments done as part of routine care.

4.1.7 Ability to understand and the willingness to sign a written informed consent document or ability to have consent provided by Legally Authorized Representative.

4.2 Exclusion Criteria:

4.2.1 Patients who do not meet above inclusion criteria are not eligible.

4.2.2 Patients may not be receiving any other investigational agents.

4.2.3 History of allergic reactions attributed to previous transfusion history.

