6.6 Correlative Studies

6.6.1 Baseline and longitudinal laboratory assessment (Appendix 2). Appendix 2 contains data elements that will be collected at both baseline and every three days while the patient is hospitalized.

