9.0 CRITERIA FOR RESPONSE ASSESSMENT

All patients will be evaluated for response based on clinical outcomes and laboratory improvement.

Clinical assessment is done daily. Laboratory evaluation is done every three days.

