10.0 MONITORING OF PATIENTS

Baseline evaluations are to be conducted the day of planned plasma infusion. At the discretion of the treating team, convalescent plasma may be held.

The recipient will be monitored for transfusion reaction in accordance with Norton Healthcare's policy which includes:

- Take vital signs (temp, pulse, blood pressure) prior to, 15 minutes after initiating and at the completion of the transfusion.
- RN, LPN, APRN, PA must remain with the patient unit the 15 min vital signs are performed and asses the patient periodically during the transfusion.

- Follow Norton Healthcare policy for Transfusion Reaction Protocol. Transfusion reactions will be reported per institutional policy.

Physical examination/clinical assessment will be done each day while on study.

Imaging will be completed at the discretion of the treatment team in response to clinical needs.

Laboratory testing as listed in Appendix 1 should be repeated every three days as part of clinical care. The frequency of overall testing should be at the discretion of the treating team.

Physical examination and laboratory recording should continue until patient no longer actively followed per section **6.4** and **6.5**.

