11.0 STATISTICAL CONSIDERATIONS

11.1 Study Design / Endpoints

This study uses a standard descriptive statistics for outcomes.

To determine the therapeutic efficacy (response rate) of convalescent plasma infusion in patients at high risk for mortality when infected by SARS-CoV-2 (COVID-19). The primary endpoint will be determined as prevention of progression to severe or life threatening COVID-19 during the current hospitalization. The primary endpoint will be assessed at discharge and by evaluating if the patient experienced the following data elements: respiratory rate $>30/\text{min}$, Blood oxygen saturation $<93\%$, partial pressure of arterial oxygen to fraction of inspired oxygen ration <300 , or received a medical diagnosis of respiratory failure, septic shock or multiple organ dysfunction/failure. This will be captured from the daily physical exam/clinical assessment done as part of routine care. See table 1.

The secondary objectives are to:

- Determine the immunologic effects of convalescent plasma infusion as measured by serial SARS-CoV-2 Ag levels through RT-PCR. This will be measured by CoV PCR collected at enrollment, day 7 and discharge.
- To measure normalization of laboratory parameters for risk as referenced in Appendix 2. Lab values outlined in appendix 2 will be documented every 3 days while the patient is hospitalized and we will evaluate labs from the time of convalescent plasma infusion to the time that lab value returns to within the institution's normal range.

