
Kentucky Blood Center, Inc. Lexington, Kentucky 40513 – 1709 FDA Registration Number 1070402
 
Properly identify intended recipient See Circular of Information for indications, contraindications, cautions, and methods of infusion. This product may transmit infectious agents. Rx Only
 
VOLUNTEER DONOR
 

 
E9747 APHERESIS COVID-19 CONVALESCENT PLASMA
 
_____ mL containing approx. _____ mL ACD-A Store at -18 C or colder
	
ABO: _____
 
C Flag: _____
 
Start Time: _____
 
PA
 
RESTICK

---	--

APPENDIX 2

Convalescent Plasma in Early Treatment of High-Risk Patients with SARS-CoV-2 (COVID-19) Infection RedCap Data Collection Form

LAB VALUES

Lab Name	Result	Units
White blood cell count		10 ³ /uL
Hemoglobin		g/dL
Platelet count		10 ³ /uL
Absolute neutrophil count		10 ³ /uL
Absolute lymphocyte count		10 ³ /uL
Absolute eosinophil count		10 ³ /uL
Sodium		mmol/L
Potassium		mmol/L
Chloride		mmol/L
Bicarbonate		mmol/L
BUN		mg/dL
Creatinine		mg/dL
ALT		U/L
AST		U/L
Alkaline Phosphatase		U/L
Total Bilirubin		mg/dL
PT/INR last tested		sec
CK		U/L
LDH		U/L
CRP		mg/dl
D-Dimer		ng/ml FEU
IL-6		
Other Pertinent Lab results, ABGs, Culture Results		
Ferritin		ng/mL

APPENDIX 2

Convalescent Plasma in Early Treatment of High-Risk Patients with SARS-CoV-2 (COVID-19) Infection RedCap Data Collection Form

CoV PCR (indicate site and date of collection)	Done prior to enrollment, at day 7, and on discharge	
--	--	--

Plasma

- Date of plasma infusion
- Plasma infusion start time
- Plasma infusion end time
- Total volume infused
- Plasma unit number infused

Radiological Results

- Radiological procedure completed: (must be able to enter multiple)
- Date Completed
- Normal/Abnormal
 - If abnormal, describe

Physical Exam (must be able to enter daily)

Date Completed

- HEENT – (column for body systems, Normal/Abnormal -- If abnormal, describe)
- Neurological
- Cardiac
- Pulmonary
- Abdominal
- Skin
- Extremities

Oxygen Use (will need to be able to have multiple entries):

- Route of Oxygen administration
- Amount of O₂
- Start Date
- Stop Date

Respiratory Status (enter daily)

- Highest respiratory rate in 24 hour period
- Lowest blood oxygen saturation in a 24 period
- Partial Pressure of Arterial Oxygen to Fraction of Inspired Oxygen Ratio, if available

APPENDIX 2

Convalescent Plasma in Early Treatment of High-Risk Patients with SARS-CoV-2 (COVID-19) Infection RedCap Data Collection Form

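### The laboratory outcome is defined only as return to normal, so new abnormality and relapse after plasma are not counted and the summary is tilted toward benefit

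*Combined protocol and SAP*

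**What the plan says.** Section 11.1 gives the aim as follows: "To measure normalization of laboratory parameters for risk as referenced in Appendix 2". Sections 1.2.2 and 11.1 then use the same sentence to say how: "we will evaluate labs from the time of convalescent plasma infusion to the time that lab value returns to within the" institution's normal range. Section 9.0 points the same way: "All patients will be evaluated for response based on clinical outcomes and laboratory improvement". None of these sections says what happens to a marker already in range at infusion, to one that leaves the range again after a first normal value, or to a patient who dies or goes home before a value normalises.

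Data capture is wider than the outcome. Section 6.6.1 states: "Appendix 2 contains data elements that will be collected at both baseline and every three days while the patient is hospitalized". Section 10.0 adds: "Physical examination and laboratory recording should continue until patient no longer actively followed per section" 6.4 and 6.5, so recording does not stop at the first normal value. Section 11.2 plans means with standard deviations, frequencies for categorical variables, and individual and group profile plots for repeated measures. It plans no hypothesis tests.

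Section 4.1.2 requires D-dimer or IL-6 above a cut-off, then adds "With any of the following" for lymphocytes, LDH, CK, CRP and ferritin, plus one clinical risk factor.

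**The concern.** An outcome that starts at an abnormal value and ends when the value comes into range can record improvement or failure to improve. It cannot record deterioration from normal. Ferritin or LDH that rises out of range after infusion, or lymphocytes that fall out of range, have nowhere to go in it. A value that is normal at one draw and abnormal at the next has already met the definition.

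The study describes no control group, and patients enter partly because markers are abnormal, so some return to range is expected whatever plasma does. A reader given only the normalisation figures would see that movement without the movement in the opposite direction. The opposite movement bears on how the laboratory course is judged, for both efficacy and safety.

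**Working it through.** The plan states no figure for this outcome and no derivation of the ceiling of 100 patients, so there is no calculation to reproduce. Three checks are possible.

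**1. How many markers can start in range.** The Appendix 2 laboratory list has 23 named tests, apart from the free-text entry and the CoV PCR. Seven match section 4.1.2: D-dimer, IL-6, lymphocytes (listed as "Absolute lymphocyte count"), LDH, CK, CRP and ferritin. That leaves 23 − 7 = 16 others.

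- Minimum past an entry threshold: 1 (D-dimer or IL-6) + 1 (of the other five) = 2.
- Risk markers that may start in range: at most 7 − 2 = 5.

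Five is an upper bound. Entry cut-offs such as LDH above 700 U/L or ferritin above 1000 ng/ml are not limits of normal. A patient below them may still be outside the institution's range, which the documents do not give.

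**2. A cohort example (all counts assumed).** Of 100 patients, 40 start with high ferritin and 20 of them normalise; 60 start in range and 20 of them become high.

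- Normalised among those abnormal at baseline: 20/40 = 50%.
- Newly abnormal among those normal at baseline: 20/60 = 33%.
- Abnormal before: 40. Abnormal after: 40 − 20 + 20 = 40.

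A summary of normalisation alone shows the 50% and not the unchanged total. The flows were chosen to cancel, so this shows what can happen, not what will.

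**3. Relapse and new abnormality over repeated draws (all rates assumed).** Take a two-state chain on three-day draws. Let *a* be the chance that an abnormal value is normal at the next draw, *b* the chance that a normal value is abnormal at the next draw, and *k* the number of draws.

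- Ever normal, starting abnormal: 1 − (1 − a)^k
- Normal at a given draw: p_new = p(1 − b) + (1 − p)a, starting from p = 0
- Ever abnormal, starting normal: 1 − (1 − b)^k

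With a = 0.2, b = 0.1, k = 5:

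- Ever normal: 1 − 0.8^5 = 67.2%.
- Normal at each draw in turn: 0.200, 0.340, 0.438, 0.507, 0.555, so 55.5% at the last draw.
- Gap due to relapse: 11.8 points.
- Ever abnormal, starting normal: 1 − 0.9^5 = 41.0%. None of these enters a return-to-normal outcome.
- Never normalised, starting abnormal: 0.8^5 = 32.8%.

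Over a = 0.1 to 0.3, b = 0.05 to 0.2 and k = 2 to 5:

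| Quantity | Lowest | Highest |
|---|---|---|
| Gap, ever normal minus normal at last draw | 0.5 points | 25 points |
| Start normal, ever abnormal | 10% | 67% |
| Start abnormal, never normal | 17% | 81% |

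If b = 0, both the gap and the new abnormality are zero. The tilt depends on markers moving out of range.

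**The case against.** The best defence is that the plan does not hide worsening. Values are recorded at baseline and every three days until follow-up ends, and 11.2 plans means with standard deviations and profile plots in which deterioration and relapse could appear. Clinical deterioration is the primary endpoint. The data form has adverse-event fields, and section 12.0 has a medical monitor review adverse events. The objective is secondary and descriptive. Its wording sets out a span of time and names no proportion or denominator, so the 20/40 above is a reading of it and not a planned statistic.

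Much of this stands. A reader might infer that the laboratory results can only look favourable. They can look poor: a marker that worsens from an abnormal start, or never returns to range, gives a low or slow normalisation result, 17% to 81% never normal in the assumed grid. A reader might also infer that worsening is invisible throughout the study, and the means and plots contradict that. Nor do the documents show that a typical patient starts with five risk markers in range; five is only what eligibility permits.

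The defence does not fill the gap. No planned frequency counts new abnormality or relapse. Section 11.2 does not say that means are given by visit, and later means would cover only patients still in hospital. Section 13.0 commits to collecting serious adverse events and transfusion reactions, and no rule links a laboratory shift to the adverse-event fields.

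**Conclusion.** The point holds as a one-sided definition of a secondary outcome. Followed as written, it leaves out new abnormality in markers that start normal and relapse after a first normal value, and so describes the laboratory course more favourably than the recorded data would. Because no tests are planned, this is a tilted description and not a biased test.

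The size cannot be fixed from the documents. The 0.5 to 25 points for relapse, and the 10% to 67% of normal-start markers that become abnormal at some draw, rest on assumed transition chances that stay constant over time and on two to five draws per patient.

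A further reading to avoid is that a two-way summary would show whether plasma works. Regression to the mean and natural recovery come from selecting on abnormal values and having no comparator, and they remain whichever summary is used. The change is still worth making, because the data are already there and the present wording names only one direction.

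**What to change.** In 1.2.2 and 11.1, for the seven eligibility markers:

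- Report a shift table of baseline by last in-hospital value, normal or abnormal by the institution's range. Give normalisation among patients abnormal at baseline beside new abnormality among patients normal at baseline, with both denominators.
- Report first normalisation together with status at the last draw, so that relapse is visible.
- Count death or discharge before normalisation as not normalised, and list the two reasons separately, because an early discharge in a recovering patient also lowers the figure.
- Treat any table of the worst post-infusion value as supplementary and show the number of draws with it. Longer stays give more chances of an abnormal value, so that table leans the other way.

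The cost is a change of wording and a few extra tables from values already collected. The normalisation figures may look less favourable.

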2.0 BACKGROUND AND RATIONALE

The morbidity and mortality of the SARS-CoV-2 (COVID-19) pandemic has been well established. Approaches to COVID-19 has focused on preventing mass spread and treating those with critical disease, while providing supportive care to mild, moderate or severe disease. The FDA has provided guidelines for the treatment of patients with convalescent plasma and this has been restricted to patients with severe or critical disease. As our understanding of the epidemiology of this syndrome continues to expand, it has become clearer that given the extremely poor outcome for those requiring mechanical ventilation and those within a few discreet categories, a therapeutic approach focused around prevention of the transition to critical status is a key to ameliorate the poor outcomes experienced to date.

2.1 SARS-CoV-2 Infection (COVID-19)

The impact of the severe acute respiratory syndrome coronavirus - 2 (SARS-CoV-2) pandemic and more specifically the associated syndrome [COVID-19], has been rapid and extreme. As of June 1, 2020 estimates for worldwide spread suggests almost 6.3 million confirmed cases, 375,000 deaths and 1.8 million confirmed cases in the United States (GISANDDATA.maps.arcgis.com). Data continues to suggest that those at greatest risk for poor outcome include the elderly and those with comorbid illness((1)(2)(3)). In fact, Zhou reports in a retrospective multivariate analysis the odds of dying in the hospital related to COVID-19 was highest with increased age, Sequential Organ Failure Assessment (SOFA) score and concomitant markers of inflammation.(4) A report of 72,314 patients in China reports

the case fatality rate (CFR) of those over 80 years of age is 14.8%, as compared to the overall CFR of 2.3%. (5) In fact, 61.5% of those with critical disease died. (6)

There is an increasing understanding of the temporal seroconversion rate in patients infected by SARS-CoV-2 virus. Zhao and colleagues reported that among 173 patients tested median seroconversion time for IgM and IgG occurred on day 12 and day 14 respectively.(7) The relationship of this conversion timeline and the best timing of plasma procurement is still to be determined. Though this data allows that between day 14 and 21 seem optimal for plasma procurement, much of the timeliness is sure to be clarified in large multicenter trials.

Most recently, the United States Food and Drug Administration has published guidelines on the emergent use of convalescent plasma in the treatment of the COVID-19 patient.(8) It was made clear that patients with severe disease as measured by a laboratory confirmed COVID-19 infection, severe or immediately life threatening COVID-19 clinical presentation, with severe being consistent with presence of dyspnea, tachypnea (respiratory frequency $\geq 30/\text{min}$), blood oxygen saturation $\leq 93\%$, partial pressure of arterial oxygen to fraction of inspired oxygen ratio < 300 , and/or lung infiltrates $> 50\%$ within 24 to 48 hours may be eligible to receive convalescent plasma through an emergent IND protocol. In this definition, life threatening disease is defined as the presence of respiratory failure, septic shock or multiple organ dysfunction.(8)

2.2 Rationale for Convalescent Plasma Infusion in COVID-19

Currently, there are no specific therapeutic agents for COVID-19 and the principal approach to the infected patient is supportive in nature. Several therapies are under investigation including Hydroxychloroquine, Remdesivir and others, but the efficacy of these agents are not fully understood.(9–11) Over the last several years, convalescent plasma has been utilized in the treatment of severe acute respiratory illness related to an array of viral infections, including corona viruses.(12)(13–17) This “passive antibody” therapy incorporates the infusion of antibodies against specific antigen, in this case, the SARS-CoV-2 virus through the use of convalescent plasma. To date, this is the only means to provide immediate immunity to infected individuals and differs from the impact of vaccination. (17)(18) The use of convalescent plasma was first considered as possible treatment during outbreaks for SARS, Avian influenza and Ebola virus in the early part of this century.(13,19) In a study of 80 patients with SARS, the use of convalescent plasma was associated with a higher rate of hospital discharge as compared with patients who did not receive convalescent plasma.(14) Accordingly, these findings encouraged the theory that the use of convalescent plasma transfusion could be beneficial in patients infected with SARS-CoV-2.(20) Recently, there has been preliminary data in the use of convalescent plasma in the treatment of 5 critically ill patients infected with SARS-CoV-2.(21) Shen and colleagues report that all 5 patients were moribund and receiving mechanical ventilation. Further, 3 of the 5 patients were ultimately able to be discharged and 2 patients remained clinically stabilized. All patients had laboratory-confirmed covid-19 and displayed acute respiratory distress syndrome (ARDS) and exhibited significant end organ dysfunction in the form of rapid clinical deterioration and the requirement for high levels of medical and ventilator support.(21)(22) In the work by Shen, the ABO blood types of the patients were determined as is standard for compatibility of donor. Each recipient received two consecutive transfusions of 200 to 250 mL of ABO-compatible convalescent plasma for a total of 400 mL. This occurred on the same day it was obtained from the donor. The Chinese team of Duan and colleagues have also published data on the use of convalescent plasma therapy in patients with COVID-19. (23) (24) They described the benefits in their study group of 10 patients where several

parameters such as c-reactive protein, lymphocyte count and viral load all showed improvement within seven days of infusion of plasma. Importantly, they reported no severe adverse effects. These results from 10 severely ill patients demonstrated that one dose of 200 mL convalescent plasma was very well tolerated and led to disappearance of clinical symptoms in 3 days and viremia in 7 days. Further, the authors suggest that treatment earlier in the disease course seemed to result in improved responsiveness.

Given this historical data of significant improvement in respiratory failure secondary to viral infection, coupled with the new case series of COVID-19 patients benefitting from convalescent plasma infusions the idea of utilization of this modality earlier in the clinical course is compelling and warrants further expansion of this safe and readily available therapy.

